The primary objective of the proposed study is to determine the impact of tDCS on pain in substance use disorder (SUD) subjects. The long-term goal of the study is to address the underlying neurobiological deficiencies caused by SUD and provide a more personalized adjunctive SUD treatment.

***Aim 1:* to compare changes in brain waves during tDCS treatment sessions in the treatment (tDCS) and placebo (sham) arms. This aim will be achieved by capturing EEG readings of the entire brain for subjects in each treatment arm at baseline, during the treatment phase, and at final study visit 1 week post treatment.**

***Aim 2:* to compare changes in self-reported pain perception in the treatment and placebo (sham) arms. We will achieve this aim by comparing the baseline pain perception scales results of subjects in treatment and placebo arms to pain perception scales results on the final day of the treatment and again one week later, enabling investigators to determine any short-term change or durable change to pain.**

***Aim 3:* to compare the safety and tolerability of the tDCS system (tKIWI) versus placebo (sham) in terms of any unwanted side effects or adverse events. We will achieve this aim by monitoring subjects’ vitals during the entire session and evaluating results of a**

IRB Protocol for Human Subjects Research

questionnaire after each treatment session and after the final study visit, enabling us to capture reported discomfort.

Our central hypothesis is that applying transcranial direct current stimulation using the patented tKIWI system will safely reduce self-reported chronic pain with little to no side effects. If this hypothesis is accurate, the next steps are to identify mechanistic biomarkers to improve our understanding and ability to accurately diagnose pain disorders which would facilitate the development of pharmacologic and non-pharmacologic treatment modalities using deep learning architecture built into the tKIWI.

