Treatments focus entirely on pharmacological and behavioral approaches without evaluating the brain itself [9,10] even though chronic pain has been shown to be significantly related to brain function [8-11]. This creates significant limitations, such as imprecise treatment modalities, medicine side effects, and decreased treatment adherence due to slow progression and increased patient frustration [12-14]. This predominant approach ignores the brain’s neuroplasticity and ability for cell-regeneration and fails to consider the individual impacts on brain regions.

Expected Endpoint / Outcome Measures: The primary efficacy endpoint in this RCT is chronic pain participants in the treatment arm feel a reduction in symptoms of pain and a self-reported reduction in opioid use, or the desire for opioid use. The primary safety endpoint of this RCT is that after both single and multiple treatments, no participants experience clinically significant side effects or adverse events.

4.0 Funding Information:

Indicate all sources of funding for the project, including gift funds, departmental funds, or other internal funding. For each funder, list the name of the funder, and the institutional proposal number or award number you received from Sponsored Projects. For externally funded projects, the information below should match the Study Funding Sources in [eIRB](#).

 No Funding	
 Federal Funding , including flow-through federal funding (i.e., NIH, NSF, DoD, etc.)	Name of funding source:
	Institutional Proposal or Award Number:
	eDoc # (for multi-site projects):
 Industry Funding	Name of funding source:
	Institutional Proposal or Award Number:
	eDoc #:
 Foundation Funding	Name of funding source:
	Institutional Proposal or Award Number:
 Department Funding	Name of funding source: Career Development Award, UAHS

IRB Protocol for Human Subjects Research

 Gift Funding	Name of funding source:
 Other	Name of funding source:

5.0 Resources Available to Conduct the Human Research:

Describe the resources (facilities, time, emergency resources, etc.) available to recruit, consent, conduct study procedures, and analyze data.

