 Cognitive or behavioral measures, including daily diaries	 Records – billing
 Data collected using other communication/electronic devices (e.g., cell phones, pagers, and texting devices)	 Records – educational
 Data previously collected for research purposes	 Records – employee
 Deception	 Records – lab, pathology and/or radiology results
X Instrumentation, equipment, or software not approved by the FDA	 Records – mental health
 Interviews – focus groups	 Records – substance abuse
 Interviews – in person	 Research imaging protocols
 Interviews – virtual/online	 Recombinant DNA
 Medical records review	 Social networking sites
 MRI/ultrasound with contrast	 Stem cells
 MRI/ultrasound without contrast	 Radiation Scans (X-Ray, CT Scans, etc.)
✓ Non-invasive instruments (e.g., external sensors applied to the body)	X Other activities or interventions – describe: We will collect EEG data, Vitals (heart rate, blood pressure, Pulse O2, respiratory rate, and temperature), responses to pain surveys (VAS and FACES) as well as responses to a cognitive evaluation (MMSE). Click or tap here to enter text.

- **Description of research procedures.**

The proposed study employs a randomized, double-blind, sham-controlled design to evaluate the effects of the tDCS using the tKIWI device on chronic pain. We will be randomly assigned to treatment (tx) or sham/placebo group.

IRB Protocol for Human Subjects Research

Up to 40 participants will be recruited and randomly placed in either the treatment or the sham group. The randomization ratio is 1:1. Each participant has an equal chance of being assigned to each condition and each participant will be assigned to a condition independently of the other participants. The sample is small (20 each group), so in order to ensure random assignment, we will assign a unique number to every participant of the study's sample. Then, we will use a lottery method to randomly assign each number to the control or experimental group.

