tDCS: The anode and cathode are two large 5 cm by 5 cm gel-based pads which are placed on the scalp. This reduces the risk of burn or irritation and increases conduction. The 2 electrodes are connected to the tKIWI device which delivers a low intensity electrical current ($\leq 2A$), thereby polarizing membrane potential of neurons in the stimulated area. Current that flows from the cathode to the anode has an inhibitory effect on the stimulated area, while current that flows from the anode to the cathode is typically excitatory. We will be initiating bilateral stimulation of the Dorsolateral pre-frontal cortex (DLPFC), which has been shown in the literature to elicit a significant decrease in ambiguous risk-taking behavior in healthy human subjects and a decrease in pain on a non-ambiguous risk task.

Both anodal and cathodal stimulation is used. Anodal is the negative or inhibiting electrode and cathode is the positive or oxidizing. tDCS is polarity-dependent.

In order to help minimize the stinging feel of the treatment, we have chosen to ramp up time and frequency. For visits 1-5 (tDCS treatment visits), we will start with .5mA ramping up to .75mA for 5 minutes. Followed by a brief (8 sec) EEG recording. Then, we will apply .75mA to 1mA for 5 minutes. This will also be followed by 8 second EEG recording. The final application of current will be 1mA to 1.75mA for 10 minutes followed again by 8 second EEG recording. The sham group will receive 1 minute from 0.0mA to no more than 0.5mA at the initiation of the treatment after which the current will be turned off. This is to maintain a blind trial. 0.5mA is negligible current, but mimics treatment with an initial small tingle. The current delivered by tDCS is not strong enough to trigger an action potential in a neuron; instead its “sub-threshold” changes the pattern of already active neurons. The device has built-in protections to prevent more than 2mA from being inadvertently administered at any time. The Clinical Trial Protocol table demonstrates the study procedures for each day.

Vitals (heart rate, pulse, blood pressure, temperature) will also be taken at the beginning and end of each treatment visit along with an open-ended verbal self-report of any side-effects, which the researcher will document in redcap.

- **Specify the total estimated time commitment for subject participation, and the estimated time commitment for each activity.**

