Individuals may reasonably expect a decrease in pain from participation in the study for the treatment group. For the sham group, they will be contributing to an innovative and non-invasive, non-habit forming, safe treatment for treatment of chronic pain, and may also receive a benefit of reduced pain from a placebo effect.

Risks to Subjects:

- **Describe all physical, psychological, social, legal, and/or economic risk that could be associated with participation in this research.**

The most common reported side effects/risks include itching, tingling, headache, burning sensation, redness and discomfort. These are similar in adults and children. The physical adverse effects are restricted to the site of stimulation [1]. Other than these reversible minor adverse effects, no severe adverse effects that were irrecoverable or required professional treatment were reported (22). tDCS is known to be safe and non-invasive and is used frequently in human clinical trials. The other potential risk to subjects is an unlikely breach of confidentiality. This will be mitigated by keeping the enrollment data (with identifiers) separate from the study data. Upon enrollment, the research staff will assign each subject a numerical “study number.” The PI and device sponsor will not have access to identifiable data once it is coded for deidentification.

- **Discuss what steps will be taken to minimize risks to subjects/data.**

There are no risks expected to subjects as tDCS in humans has been widely studied for over a decade; however, to ensure that we document the lack of risks, we will be monitoring heart rate,

IRB Protocol for Human Subjects Research

blood pressure, pulseO2, respiratory rates, and temperature at baseline and post treatment. We will also ask the subjects for self-report of any adverse events or issues that may have arisen.

- **Describe any costs, monetary and non-monetary, that subjects may incur. This includes time.**

There is no monetary cost for subjects other than possible cost to transport themselves to the lab. There is a time commitment, however, and it is required that the subject be able to transport themselves to the study site. There are a total of 7 visits within 3 weeks that subjects will have to make the time for (including transportation time and time spent in the study). The subject will commit to 11 days of coming into the lab over a 3 week period.

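### The primary safety endpoint is a zero-event rule with no stated arm and no sham comparison, so it does not match Aim 3 or the test planned for it

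*Combined protocol and SAP*

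**What the plan says.** Under Expected Endpoint / Outcome Measures in section 3.0 Purpose, the primary safety endpoint is that "after both single and multiple treatments, no participants experience clinically significant side effects or adverse events". The sentence just before it, on efficacy, does name an arm: it asks whether "chronic pain participants in the treatment arm feel a reduction in symptoms of pain". The safety sentence names none.

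Aim 3, in the same section, is comparative: "to compare the safety and tolerability of the tDCS system (tKIWI) versus placebo (sham"). The Data Analysis text in section 10.0 gives Aim 3 a chi-square or Fisher exact test. It states no significance level, sidedness or margin, and does not connect the test to the primary safety endpoint.

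On numbers, section 10.0 says "Up to 40 participants will be recruited and randomly placed in either the treatment or the sham group", "The randomization ratio is 1:1" and "The sample is small (20 each group").

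Two further statements bear on what might count as an event. The tDCS Application text says of the sham current that "0.5mA is negligible current, but mimics treatment with an initial small tingle". The Risks to Subjects text says "The most common reported side effects/risks include itching, tingling, headache, burning sensation, redness and discomfort", and goes on to treat these as minor and reversible. Neither *clinically significant* nor an expected event rate is defined anywhere.

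**The concern.** As worded, the endpoint is a pass/fail rule whose only input is whether the event count is zero. The sham rate does not enter it. One background event, such as an unrelated illness during the study period, fails a device that does no harm. On the plain reading, an event in a sham participant does so too.

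The plan also has two safety criteria that can disagree. A single sham event could fail the primary endpoint while the Aim 3 comparison shows nothing against the device. The plan does not say which result governs the safety conclusion, although the randomised sham arm exists to separate device effects from background.

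**Working it through.** **Inputs from the documents:** up to 40 participants, 1:1, 20 per arm (section 10.0); success means zero qualifying events (section 3.0). The plan has no safety figure to reproduce: it gives no event rate, significance level or sample-size calculation.

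**Assumption:** each participant independently has chance p of a qualifying event over the study. Because p is not given, a range is shown.

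**Step 1: who counts.** The efficacy sentence names the treatment arm and the safety sentence does not. Section 10.0 uses the word participants for everyone randomised, and the timeline in section 5.0 applies the term treatment session to sham sessions as well. The plain reading is therefore all 40. The text does not say so literally, so both readings are carried.

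**Step 2: harmless device, same p in both arms.** P(fail) = 1-(1-p)^n. For example, at p = 2%, 1-0.98^40 = 55% and 1-0.98^20 = 33%. On the 40-participant reading, the chance that sham events alone cause failure is (1-p)^20 × [1-(1-p)^20].

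| Assumed p | Fails, all 40 count | Fails, 20 treated count | Fails from sham events alone (40 count) |
|---|---|---|---|
| 0.5% | 18% | 10% | 9% |
| 1% | 33% | 18% | 15% |
| 2% | 55% | 33% | 22% |
| 5% | 87% | 64% | 23% |
| 10% | 98.5% | 88% | 11% |

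**Step 3: harmful device at the same background rate.** P(fail) = 1-(1-p_sham)^20 × (1-p_tx)^20.

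- 5% background, treatment-arm rate 15%: 1-0.95^20 × 0.85^20 = 98.6%, against 87% if harmless. Counting only the treated, 1-0.85^20 = 96%, against 64%.
- 1% background, treatment-arm rate 6%: 1-0.99^20 × 0.94^20 = 76%, against 33% if harmless.

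On the 40-participant reading, the rule discriminates weakly at a 5% background rate and better at 1%.

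**Step 4: the comparison already planned.** With Fisher's exact test on 20 v 20 (two-sided 0.05, assumed), a harmless device is flagged 0.01%, 0.2% and 1.2% of the time at background rates of 2%, 5% and 10%. Power is 7% for 5% v 15%, 30% for 5% v 25% and 72% for 5% v 40%. With no sham events, 5 of 20 treated are needed for significance (p = 0.047). The test seldom condemns a harmless device but misses moderate harm, which is why an interval should accompany it.

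**The case against.** The strongest reply is that the plan already compares the arms. Aim 3 and its Fisher test do so, and the zero-event sentence sits under expected endpoints with no stopping rule or go/no-go decision attached. This stands in part: device harm can be examined in this trial. It does not remove the mismatch between the endpoint labelled primary and that comparison.

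A second reply is that only treated participants were meant. That is possible. Sham events would then not count, and the failure probabilities fall to the 20-participant column. Background events in treated participants would still fail a harmless device, and there would still be no comparator.

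A third is that events grave enough to be *clinically significant* are rare in so short a study. The documents support no particular rate, and 5% or 10% may be too high. At 0.5% a harmless device still fails 18% or 10% of the time, depending on who counts.

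Two stronger inferences are tempting and should not be drawn:

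- **That a harmless device could fail more often than a harmful one.** This appears only if a harmless device at 5% background (pass probability 0.95^40 = 13%) is set against a device that harms 5% of treated participants at zero background (0.95^20 = 36%). Those are different populations. At a fixed background rate, added harm can only raise the failure probability.
- **That the rule fails almost by construction because the sham is meant to tingle.** This needs *clinically significant* to qualify side effects but not adverse events. The more natural reading covers both, and the Risks to Subjects text treats the listed sensations as minor.

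**Conclusion.** The point holds as a flaw in the stated rule. The primary safety endpoint is an absolute zero-event criterion with no named arm and no use of sham, and it is not aligned with Aim 3 or the Data Analysis text. At assumed background rates of 1% to 10%, a harmless device fails with probability 33% to 98.5% if all 40 count, or 18% to 88% if only the 20 treated count. These figures rest on assumed, independent and equal event rates and on full enrolment; fewer participants would lower them.

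A reader might infer that the trial cannot assess device harm at all. The documents do not support that, because the between-arm comparison is planned. The wording should be corrected before unblinding, but the design need not change.

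**What to change.** Replace the safety sentence in section 3.0 with wording such as:

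*The primary safety endpoint is the proportion of participants with at least one clinically significant side effect or clinically significant adverse event, compared between tDCS and sham as a risk difference with a 95% confidence interval, alongside Fisher's exact test.*

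Then:

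- Drop the absence of any event as the success criterion.
- Define *clinically significant*, and make clear that it applies to both side effects and adverse events.
- Summarise the expected transient sensations listed under Risks to Subjects separately by arm.
- Count events over V1 to V5, where Table 2 schedules the side-effect survey. Add the final visit once the documents agree on it: Aim 3 refers to a questionnaire after that visit, but Table 2 lists none.

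The cost is mainly wording, since both arms and the V1 to V5 survey are already in the plan. Including the final visit may mean adding a survey to the schedule. The simple claim of no events is lost as a criterion, and the interval will be wide. As a rough guide at observed rates of 5% and 15%, the Wald half-width is 1.96 × √(0.05×0.95/20 + 0.15×0.85/20) = 18 percentage points. An interval method suited to small counts should be named in the plan.

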	Publish	Month 16	
 Publish findings in an academic journal Present findings internally and at conference Plan for next phase of clinical trial Publish biomarkers data in academic journal
	Transition	Month 17+	
 Prepare and submit R01

6.0 Study Population:

- Select all the categories of participants included in the research:

 Healthy adults	 Non-English-speaking subjects
 Non-healthy adults	 UA staff/faculty
 Children (under 18 years old) *	 UA students
 Pregnant women, neonates, and/or fetuses*	 Banner employees
 Prisoners*	 Refugees
 Native Americans, Alaskan Native, and Indigenous Populations*	 Other – please explain: Adults ages 18-79 with a self-reported history or diagnosis of chronic pain (>3mo)
 Adults unable to consent (i.e., cognitively impaired adults) *	

- For each of the above selected categories, describe the inclusion and exclusion criteria. Indicate age range, gender, and ethnicity.

Inclusion Criteria:

Age: 18-79 years old

Gender: Any

Ethnicity: Any

Chronic pain (\geq 3-months); No current use of nonprescription opioids (\leq 1 month); Able and willing to comply with scheduled visits and other study-related procedures to complete the study; Willing and able to give informed consent.

Exclusion Criteria:

- Diagnosis (as defined by DSM-IV) of: any psychotic disorder (lifetime); eating disorder (current or within the past year); obsessive compulsive disorder (lifetime); mental retardation.

IRB Protocol for Human Subjects Research

- History of drug or alcohol abuse or dependence (as per DSM-IV criteria) within the last 3 months (except nicotine and caffeine).
- Subject is on regular benzodiazepine medication which it is not clinically appropriate to discontinue.
- Subject requires a rapid clinical response due to inanition, psychosis or high suicide risk.
- Neurological disorder or insult, e.g., recent stroke (CVA), which places subject at risk of seizure or neuronal damage with tDCS.
- Subject has metal in the cranium, skull defects, or skin lesions on scalp (cuts, abrasions, rash) at proposed electrode sites.
- Female subject who is pregnant.

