- Participants who are not fluent in English will not be included in the trial for safety reasons: a) It is usually not possible to have an interpreter reliably available every weekday for up to 4 weeks and it is not safe to give tDCS to a subject who cannot tell us immediately of any side effects; Note that translation of the proposed ACT activity into English has not been validated and that we cannot be confident that they would be accurately translated and validated.
- Minors
- Older than 79 years old
- last use >24 months
- history of EEG or any electrical implant (i.e. pacemaker)
- history of Parkinson's, diagnosis of bipolar, schizophrenia/schizo-affective d/o, OCD, epilepsy, alzheimers
- taking antipsychotic drugs

One of the exclusion criteria is recent history of drug abuse or dependence (in the last 3 months). This would include prescription or non-prescription. If someone uses an opioid (prescribed or not) and does not meet that exclusion criteria, they are eligible to participate for that criteria. We would request that if possible, they refrain from using an opioid within a 3 hours of their appointment.

- **Describe the total number of subjects to be enrolled locally. If obtaining specimens, specify the maximum number of specimens needed for this project.**

The total number of subjects to be enrolled locally is 40 subjects.

7.0 Recruitment Methods:

- **Select the methods used to recruit individuals.**

 Email	 Screening of the Electronic Medical Record (EMR)
 Face to face	 Social media
 Flyers	 SONA System
 In person presentations	 TV, Radio, Print

IRB Protocol for Human Subjects Research

 Online advertisements	 Other – please explain: Click or tap here to enter text.
 Phone calls	

- **Explain the recruitment process. Describe how potential subjects will be identified, where recruitment will take place, when recruitment will occur, and the methods that will be used to recruit individuals.**

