Recruitment Location(s): We plan to recruit participants from clinical settings in Tucson, Arizona, such as the Veterans Affairs Hospital and private clinics and hospitals, private enterprises, such as gyms and health-related facilities (chiropractic offices, yoga/pilates studios). We also plan to recruit participants via local Facebook/Instagram and Twitter.

Recruitment Method(s): Recruitment flyers will be distributed to several health clinics and settings. Additionally, ads will be placed on Facebook and Twitter. At this time, we do not plan to conduct in-person recruitment. The flyers will include a link and QR code to a simple Qualtrics form where the interested person will be able to include their name and contact information. Potential participants will then be contacted to schedule an initial visit.

Site authorizations will be sought for each place we put flyers.

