The screening will be in redcap where the potential participant will respond to inclusion and exclusion criteria. If the participant is eligible, they will be emailed or provided the consent and enrolled in the study. They will sign the consent during their first visit where demographic data will also be collected and entered into Qualtrics.

Demographics Collected will include:

- Age
- Sex
- Race/Ethnicity
- City, State, Zip
- Phone
- Email
- First Drug Use
- Most Recent Drug Use
- Preferred/Most commonly used drug
- Mental Health diagnoses (including SUD)

The study will occur in 7 visits over an 11 day-period. (see table 2). At the beginning of each visit, the participants will answer a very brief “Pre-Study Session Update” survey to ensure no changes to eligibility have occurred between visits.

Visit 0 will consist of informed consent review and signature, collection of demographic data, baseline self-report pain using the pain surveys (FACES and VAS), brief cognitive survey (MMSE), and baseline EEG recording.

Visits 1-5 will consist of initial EEG recording, three sessions of ramped up tDCS followed by EEG recording and self report pain surveys. Session 1 will be 5 minutes, session 2 will be 5 minutes, and session 3 will be 10 minutes. Details on mAs are listed under tDCS application. The final post visit (V7), on day 11 will consist of no treatment, but a repeat of the data collected on Visit 0.

The visits will take place in [name] lab, room 645 in the UArizona Life Sciences Building. This laboratory is approximately 600sq/ft in size. All [name]’s labs are located next to each other in the Life Sciences North building (Rms 632, 621, 619, 614, 615, 601). All biohazards are disposed according to institutional guidelines. Through [name], we will also have access to shared laboratories that include a molecular biology laboratory of 1,000 sq. ft, an analytical laboratory of 1500 sq. ft. and a radioligand binding laboratory of 1,000 sq. ft. The laboratories include seating space for students and research personnel.

Clinical Trial Protocol: Baseline V0, Tx V0-5, Post V7 (11 days)	
⇒	Pre-Questionnaire (15 min) 
 ○ Cognitive Eval (MMSE) ○ Rate Pain (VAS & FACES) ○ Record medication, activity, symptomology past 24 hours
⇒	Monitor vitals (5 min) 
 ○ HR, BP, PulseO², respiratory, temp, etc (set up continuous measure) ○ Put on device and log into patient portal
⇒	EEG Recording (5 minutes)

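### Entry sets a duration of chronic pain but no minimum current pain, so people with little room to improve can be randomised and power on the pain comparison is lost

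*Combined protocol and SAP*

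**What the plan says.** Section 6.0 (Study Population) describes pain at entry in two places. The label beside the ticked population category reads "Adults ages 18-79 with a self-reported history or diagnosis of chronic pain (>3mo". The inclusion list reads "Chronic pain (\geq 3-months); No current use of nonprescription opioids (\leq 1 month". Both give a duration. Neither gives an intensity, a frequency or a recall window. The exclusion list contains no pain score.

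Section 10.0 says how eligibility is established: "The screening will be in redcap where the potential participant will respond to inclusion and exclusion criteria". Visit 0 then collects "baseline self-report pain using the pain surveys (FACES and VAS", with no cut-off attached, and Table 2 adds none. Later visits open with a short "survey to ensure no changes to eligibility have occurred between visits", which can only recheck the existing criteria.

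Section 7.0 lists clinics and hospitals, social media, and "private enterprises, such as gyms and health-related facilities (chiropractic offices, yoga/pilates studios" as recruitment sources. Opioid users who do not meet the abuse or dependence exclusion may enter, and Section 6.0 says of them: "We would request that if possible, they refrain from using an opioid within a 3 hours of their appointment".

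In Section 3.0 the primary efficacy endpoint is that "chronic pain participants in the treatment arm feel a reduction in symptoms of pain", together with less opioid use or less desire for opioids. The Data Analysis part of Section 10.0 tests Aim 2 with a two-sample t-test on change in self-reported pain, between arms and also within a group from baseline to post-study. It states no baseline adjustment. Allocation is by 1:1 lottery, 20 per arm, with no stratification.

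**The concern.** Change in pain is the only efficacy outcome with a planned test. A participant who rates 5 on a 100-point scale at Visit 0 can improve by at most 5 points, whichever arm they are in. If a noticeable share of the 40 are like this, the average difference between tDCS and sham shrinks and a working device may look ineffective.

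Several features make such enrolment plausible. The sources reach beyond pain clinics, eligibility is self-answered, and pain may be masked by analgesia when it is rated. Section 5.0 says the results will feed the next trial phase and a grant application, so a diluted estimate would carry forward.

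**Working it through.** **The plan's own figure.** Section 6.0 gives a total of 40, and Section 10.0 gives 20 per arm. No alpha, power, effect size, SD or dropout is stated, so the 40 cannot be reproduced. Everything below is illustration on assumed inputs: two-sided 5%, no dropout, and a share f of low-pain participants from 0 to 30%.

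**Check 1: pure dilution.** Assume low-pain participants show no treatment effect and the SD is unchanged. A standardised effect d becomes d(1 - f). For a two-sample t-test with n = 20 per arm there are 38 degrees of freedom, the critical value is 2.024, and the noncentrality is d(1 - f) × √(20/2). An assumed d = 0.90 gives about 79% power with nobody at the floor.

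| f | d(1 - f) | noncentrality | power | sample inflation 1/(1 - f)² |
|---|---|---|---|---|
| 0 | 0.90 | 2.85 | 79% | 1.00 |
| 10% | 0.81 | 2.56 | 70% | 1.23 |
| 20% | 0.72 | 2.28 | 60% | 1.56 |
| 30% | 0.63 | 1.99 | 49% | 2.04 |

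Other assumed effects (normal approximation), from f = 0 to f = 30%: d = 0.5, 35% to 20%; d = 0.8, 72% to 43%; d = 1.0, 88% to 60%.

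**Check 2: floor simulation.** This version lets low-pain participants move a little and also lowers the variance. Assumed inputs on a 0-100 VAS:
- low-pain baselines uniform from 0 to 10; other baselines mean 55, SD 18
- sham improvement 8 points, additional tDCS effect 20, noise SD 22
- scores cut off at 0 and 100

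With 20,000 simulated trials per setting, power is 77%, 73%, 67% and 62% at f = 0, 10, 20 and 30%. Other random seeds agree to within about 1 point. The mean between-arm difference falls from 17.7 points to 14.1 at f = 30%.

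**Check 3: is the comparison biased?** With the tDCS effect set to zero in the same simulation, the t-test rejects in about 5% of trials at every f. Allocation balances low-pain participants on average. Chance imbalance is still possible in one trial: if 8 of 40 are low-pain and arms are exactly 20 and 20, the hypergeometric probability of a 6-2 or more uneven split is 0.235. That is part of the sampling error and not a systematic distortion.

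**Check 4: side effect of gating on the baseline score.** Selecting on a noisy reading makes the next reading fall without treatment. Assume true mean 45, between-person SD 18, within-person SD 15 and a cut at 40 (used only to show the mechanism).
- Observed SD = √(18² + 15²) = 23.4.
- Standardised cut a = (40 - 45)/23.4 = -0.213.
- φ(a)/(1 - Φ(a)) = 0.667.
- Expected fall = 15²/23.4 × 0.667 = 6.4 points.

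Both arms share this fall, so it cancels between arms but inflates the within-group comparison.

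**The case against.** The strongest reply is that the text points to people with present pain. The inclusion item names chronic pain as a condition the person has. The timeline in Section 5.0 speaks of chronic pain patients, and Section 8.1 describes recruits as people looking for treatment for it. A reader might infer from the population label that a past history alone is enough, so that someone in remission qualifies. The documents do not support that as the operative rule. The label and the inclusion item are worded differently and should be aligned. What survives is that current pain, even if required, has no minimum intensity.

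A reader might also infer that low-pain participants cannot show any reduction and contribute nothing. That is strict only at a score of 0; mild pain can still fall a little. Table 2 also has pain rated before and after each treatment session, so Visit 0 is not the only reading. The endpoint's opioid component is not at a floor merely because pain is low, although opioid use is not an entry requirement and no analysis of it is described. The EEG and safety aims do not need a high pain score.

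A third tempting reading is that uneven numbers of low-pain participants bias the result. Check 3 shows otherwise. Finally, broad entry can be a legitimate choice in a small department-funded study. It would then need to be stated and its power cost accepted, and the plan does neither.

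**Conclusion.** The concern holds as a loss of power. The pain criterion is duration only, no score gates randomisation, and the planned analysis does nothing to offset participants with little room to improve.

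The absence of a cut-off is certain from the text. The size of the loss is not, because the documents give no low-pain share, effect size or SD. With an assumed 30% low-pain share and an effect giving about 77-79% power without them, power falls to about 49% under pure dilution or about 62% in the floor simulation. A claim that the sample would have to double rests on the harsher model alone (2.04 at f = 30%) and should not be read as a finding about this trial. The comparison between arms remains valid.

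**What to change.** 1. Reword the population label in Section 6.0 to match the inclusion item, so that current chronic pain is required and a history alone is not enough.
2. Add a minimum current pain score to the inclusion criteria. The investigators should choose and justify the threshold, the scale with its range (the documents do not state the VAS range) and the recall window. The check must come before randomisation, using the rating already planned at Visit 0 or a question added to the existing REDCap screen.
3. State that people who fail the check are not randomised and do not count towards the 40. This needs saying because Section 10.0 has eligible respondents enrolled after the REDCap screen, and Section 6.0 counts the 40 as enrolled.
4. Base the efficacy conclusion on the between-arm comparison adjusted for baseline pain. Report the within-group pre-post change as descriptive only, because selection on a high baseline score would inflate it (Check 4). Adjustment also deals with chance imbalance, but it does not restore room to improve, so it does not replace item 2.

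If the investigators prefer no minimum, they should say why and still make the change in item 4.

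The cost is some screen failures, somewhat slower recruitment, and results that apply only to people with at least the chosen level of current pain. The number of screen failures depends on the threshold: under the assumed inputs of Check 4, Φ(-0.213) = 42% of candidates would fall below the cut. No new instrument is needed.
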